Participating subjects will be encouraged to contact the clinic between visits if they experience adverse events (AEs), worsening of their condition or have any other concerns. If needed, unscheduled visits will be conducted at investigator's discretion.

A schedule of study assessments is available in [Table 1](#).

Treatment with inhaled molgramostim will be given at a dosage of 300 µg once daily for 48 weeks. All subjects in the trial initially consented to 24 weeks of treatment. All enrolled subjects continuing with 48 weeks of treatment will re-consent and follow the visits schedule as described above.

Subjects that do not wish to continue to 48 weeks of treatment will end treatment after 24 weeks (visit 8) and will attend the follow-up visit 12-weeks later as per the visit schedule outlined in Protocol Version 2.0 or 3.0.

Subjects who complete the initial 24-week treatment period prior to the approval of Protocol Version 4.0 will proceed to the 12 week follow up as per the visit schedule in Protocol Version 2.0 or 3.0. Once Protocol Version 4.0 is approved they will be asked to re consent and re-initiate treatment. This will occur at the next trial visit or at an unscheduled visit. These subjects will not receive the whole 48-week treatment. They will receive treatment for an additional 24 weeks minus the number of weeks that they have been in follow up.

Subjects that do not wish to re consent and re initiate treatment will stay in follow up and attend the follow-up visit as per the visit schedule outlined in Protocol Version 2.0 or 3.0.

At Baseline and at Weeks 4, 12, 24, 32 and 40 (Visits 2, 3, 5, 8, 10 and 12), dosing will take place in the clinic after blood sampling. A data review was conducted after the first 6 subjects had completed 12 weeks of treatment. If safety concerns or poor tolerability were identified in this review, the review committee might decide on less frequent dosing for subsequent subjects

in the study. The review was conducted on 16 September 2018 and concluded that there were no safety issues of significant concern and the dose was unchanged. In order to obtain more robust treatment responses it was decided to extend the treatment duration from 24 to 48 weeks. Any changes to the conduct of the study such as change of dose, dose regimen or duration will be documented in a protocol amendment.

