### **9.3. Subject Withdrawal Criteria**

#### **9.3.1. Discontinuation from Trial Treatment**

Subjects may be discontinued from treatment and assessments at any time, if deemed necessary by the investigator.

Potential reasons for discontinuation of treatment are:

- Lack of efficacy/worsening of disease
- Unacceptable AE
- Serious hypersensitivity reaction
- Pregnancy

Those who discontinue treatment will not automatically be withdrawn from the trial but will be encouraged to continue to follow the same visit schedule. For example: if treatment is discontinued at Week 4 (Visit 3) the subject will be encouraged to attend the remaining visits.

The reason and date the subject is discontinued from treatment will be documented in the electronic case report form (eCRF).

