2. PROJECT OVERVIEW

2.1 Study Design

This is an open-label, non-controlled, multicentre, pilot clinical trial of inhaled molgramostim in subjects with persistent pulmonary NTM infection.

The study will comprise a Screening Visit, Baseline Visit, a 48-week treatment period and a 12-week follow up period. The Screening Visit (Visit 1) will be conducted up to 10 weeks prior to the Baseline Visit (Visit 2) to determine eligibility. Adult subjects with a history of chronic NTM infection with at least 2 positive cultures in the prior two years, of which at least one is within the last 6 months prior to Screening, will be considered for enrolment. Subjects should provide a positive NTM sputum culture at Screening to be eligible.

The study will include 30 subjects.

The treatment period will consist of 14 trial visits (Screening, Baseline, and at Weeks 4, 8, 12, 16, 20, 24, 28, 32, 36, 40, 44, and 48; Visits 1-14) and a follow-up visit (Visit 15) 12 weeks after end of treatment. The visits at Weeks 28, 36 and 44 (Visits 9, 11 and 13) will include a telephone contact, all other visits will include a clinic visit.

At the Baseline Visit (Visit 2), eligible subjects will start treatment with inhaled molgramostim administered via the PARI eFlow nebulizer.

At each visit (Visits 1-15), sputum samples for staining and microscopy, and microbiological culture will be collected. If required, induced sputum may be obtained according to local standards. On the days of clinic visits (Visits 1, 2, 3, 4, 5, 6, 7, 8, 10, 12, 14 and 15), subjects will be asked to collect two additional sputum samples at home, preferably on the consecutive days after the site visit (At the commencement of the study, only 1 sample was required for Visits 2 to 7, with the additional sampling added in protocol amendment(s)). On the days of the telephone contact visits (Visits 9, 11 and 13), three sputum samples will be collected at home, preferably on consecutive days.

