Subjects that do not wish to continue to 48 weeks of treatment will end treatment after 24 weeks (visit 8) and will attend the follow-up visit 12-weeks later as per the visit schedule outlined in Protocol Version 2.0 or 3.0.

Subjects who complete the initial 24-week treatment period prior to the approval of Protocol Version 4.0 will proceed to the 12-week follow up as per the visit schedule in Protocol Version 2.0 or 3.0. Once Protocol Version 4.0 is approved they will be asked to re consent and re-initiate treatment. This will occur at the next trial visit or at an unscheduled visit. These subjects will not receive the whole 48-week treatment. They will receive treatment for an additional 24 weeks minus the number of weeks that they have been in follow up.

Subjects that do not wish to re consent and re initiate treatment will stay in follow up and attend the follow-up visit as per the visit schedule outlined in Protocol Version 2.0 or 3.0.

At Baseline and at Weeks 4, 12, 24, 32 and 40 (Visits 2, 3, 5, 8, 10 and 12), dosing will take place in the clinic after blood sampling. A data review was conducted after the first 6 subjects had completed 12 weeks of treatment. If safety concerns or poor tolerability were identified in this review, the review committee might decide on less frequent dosing for subsequent subjects in the study. The review was conducted on 16 September 2018 and concluded that there were no safety issues of significant concern and the dose was unchanged. In order to obtain more robust treatment responses it was decided to extend the treatment duration from 24 to 48 weeks. Any changes to the conduct of the study such as change of dose, dose regimen or duration will be documented in a protocol amendment.

During the study, subjects in Group 1 will continue use of antimycobacterial treatment. All changes in antimycobacterial treatment will be recorded, including reasons for each change. In case of worsening of NTM pulmonary disease, antimycobacterial treatment may be added or a dosage increase of antimycobacterial treatment may be applied as rescue treatment, according to investigator's discretion.

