3.3.2 Study Terminology

Study-specific standard terms are detailed in Table 3.

Table 3: Study CDISC Terminology

Subject Elements	Screen (SCRN) Molgramostim (MOLG) Follow-Up (FU)
Epochs	SCREENING OPEN LABEL TREATMENT FOLLOW-UP
Treatment Arms	GROUP 1 GROUP 2
Visit Numbers / Visits	
SCREENING EPOCH
 
1.0 Screening
 
TREATMENT EPOCH
 
2.0 Baseline Visit*
 
3.0 Week 4
 
4.0 Week 8
 
5.0 Week 12
 
6.0 Week 16
 
7.0 Week 20
 
8.0 Week 24
 
9.0 Week 28
 
10.0 Week 32
 
11.0 Week 36
 
12.0 Week 40
 
13.0 Week 44
 
14.0 Week 48
 
888 Early Discontinuation
 
999 End of Study
 
FOLLOW-UP EPOCH
 
15.0 Follow Up Visit
 
Unscheduled visits: x.n where x is the visit number of the closest previous scheduled visit and n is the sequence number of the unscheduled visit, restarting at 1 after each scheduled visit. EPOCH will be assigned according to the epoch of the closest previous visit.
 
* “Baseline Visit” will be used when referring to Visit 2. The term “Baseline” will also be used as detailed in 3.3.3.

3.3.3 **Baseline**

For sputum data, baseline will be derived from the combined pre-treatment visits (i.e. Screening and Baseline), where at least one positive sample will be assigned as positive as baseline. For gradings, the most severe/highest grade will be used.

For all other parameters, baseline will be defined as the last available assessment prior to first study drug administration.

3.3.4 **Change from Baseline**

Absolute change from Baseline will be calculated as:

$$\text{Absolute change from baseline} = (\text{postbaseline value}) - \text{baseline value}$$

3.3.5 **Listings, Tables and Figures**

Listings, tables and figures will be delivered as individual .rtf files in accordance with the mock listings, tables and figures.

Data listings will present all data, with subjects grouped by Group.

Tabulations will summarise data by Group and Total.

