9.2 Variables

9.2.1 *Primary Endpoint Variables*

- Sputum culture conversion during the treatment period defined as all available samples from three consecutive visits to be negative
- The time of culture conversion: Defined as the time the first of three consecutive visits with 100% negative samples was obtained. Subjects with no conversion will be censored at the date of their last visit.

9.2.2 *Secondary Endpoint Variables*

- Sputum smear conversion: Defined as at least three consecutive visits with 100% negative AFB stained sputum smears on microscopy during the treatment period in subjects that were smear positive at Baseline.
- Durability of sputum culture conversion: Defined as conversion at or before Week 48 and culture still negative at 12-weeks follow-up (with no positives in between).
- Durability of sputum smear conversion: Defined as conversion at or before Week 48 and smear still negative at 12-weeks follow-up (with no positives in between).
- Change from baseline in semi-quantitative grade of number of NTM on microscopy of AFB stained sputum smears
- Change from baseline in semi-quantitative grade of sputum cultures (measured by time to positivity and exploratory quantitation of cultures)
- Change from baseline in symptom scores
 - Lower Respiratory Tract Infections – Visual Analogue Score (LRTI-VAS)
 - Quality of Life Questionnaire – Bronchiectasis (QOL-B)
- Change from baseline in Global Rating of Health (GRH)
- Change from baseline in body weight
- Change from baseline in 6MWD, oxygen desaturation and Borg CR10 scores

9.3 **Biostatistical methods**

9.3.1 *Primary Endpoint*

9.3.1.1 *Sputum Culture Conversion*

Sputum culture conversion data will be listed, including time of culture conversion.

Sputum culture conversion rates (number of subjects who convert to negative out of the number per group) will be presented with 95% exact binomial confidence intervals.

On the basis of the poor historical success rates of current standard therapy, a 30% response rate for the primary endpoint will be considered clinically relevant.

Time to culture conversion will be evaluated using Kaplan Meier estimates, with 95% confidence intervals.

9.3.1.2 *Sensitivity Analyses*

In a sensitivity analysis, culture conversion will be re-defined as requiring at least 2 samples are available from each of the three consecutive visits. Sputum culture conversion rates and time to culture conversion will be analysed as part of this sensitivity analysis.

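### Read together, the plan's rules let three negative visits wholly after molgramostim was stopped count as a primary conversion, and nothing separates these from on-drug conversions

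*SAP*

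**What the plan says.** **Endpoint.** SAP 9.2.1 defines the primary variable as "Sputum culture conversion during the treatment period defined as all available samples from three consecutive visits to be negative". It sets no condition on drug exposure. Non-converters are censored at their last visit, not when the drug is stopped.

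**Treatment period.** SAP 2.1, repeating Protocol 8.1, describes it by visits: "The treatment period will consist of 14 trial visits", running to Week 48. SAP Table 3 (Section 3.3.2) places Visits 2 to 14 under "TREATMENT EPOCH" by visit number. Of the numbered visits after Screening, only Visit 15 is in follow-up.

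**Stopping the drug.** Protocol 9.3.1 states: "Those who discontinue treatment will not automatically be withdrawn from the trial but will be encouraged to continue to follow the same visit schedule". Its example is a subject who stops at Week 4 and is encouraged to attend all later visits.

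**Other treatment.** SAP 2.1 says "During the study, subjects in Group 1 will continue use of antimycobacterial treatment". For worsening disease in either group, "antimycobacterial treatment may be added or a dosage increase of antimycobacterial treatment may be applied as rescue treatment". The primary variable has no rule for either.

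**Analyses.** The only analysis set is the FAS, meaning all enrolled subjects (SAP 4.1.1). The only sensitivity analysis of the primary endpoint (SAP 9.3.1.2) concerns the number of samples per visit. SAP 9.3.1.1 calls a 30% response rate clinically relevant and presents rates by group with exact 95% intervals.

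**The concern.** The primary objective is the efficacy of inhaled molgramostim on culture conversion. With no comparator, the conversion rate is the main evidence for it. A conversion whose three visits all follow the last dose is weaker evidence for the drug than one achieved while taking it. In Group 1 the background regimen was still running. In either group, antibiotics may have been added because the disease worsened, and lack of efficacy or worsening is itself a listed reason for stopping molgramostim (Protocol 9.3.1).

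A subject could therefore do poorly on the drug, stop it, receive rescue antibiotics, convert, and enter the numerator. The planned tables would not show this. SAP 9.3.2.1 carries the same approach over to smear conversion.

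**Working it through.** The plan gives no figure to reproduce: there is no sample-size calculation, dropout assumption or background conversion rate.

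**Step 1. One hypothetical subject.** A Group 1 subject stops molgramostim at Week 4, keeps attending and stays on background antibiotics. All available samples are negative at Weeks 20, 24 and 28. These are Visits 7, 8 and 9, all within the treatment epoch and the visit list. The SAP 9.2.1 condition is met and the subject is in the FAS, so this is a primary conversion timed at Week 20. Nothing in SAP 9.3.1 would reclassify it.

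**Step 2. How many runs can be off drug.** Post-baseline visits in the period fall at Weeks 4, 8, …, 48, which is 12 visits. A sequence of m visits holds m − 2 runs of three, so there are 12 − 2 = 10 runs. The stop is taken to occur at the visit shown, and the subject is assumed to keep the 48-week schedule.

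| Drug stopped at | Later visits | Runs wholly off drug | Runs wholly on drug | Mixed runs |
|---|---|---|---|---|
| Week 4 | 11 | 9 | 0 | 1 |
| Week 12 | 9 | 7 | 1 | 2 |
| Week 24 | 6 | 4 | 4 | 2 |
| Week 36 | 3 | 1 | 7 | 2 |
| Week 40 | 2 | 0 | 8 | 2 |

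If the Baseline Visit is also counted, as Table 3 taken literally would allow, there are 13 visits and 11 runs. The number wholly off drug after a Week 4 stop is still 9. Runs overlap and are correlated, so these counts show opportunity, not probability.

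**Step 3. What one conversion is worth.** The plan is for 30 subjects and the split between groups is not stated, so group sizes are assumed. Each row starts at the smallest count that reaches 30% and removes one conversion. Intervals are exact (Clopper-Pearson) 95%.

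| n | Counted | One fewer | Change in points |
|---|---|---|---|
| 10 | 3/10 = 30.0% (6.7–65.2) | 2/10 = 20.0% (2.5–55.6) | 10.0 |
| 15 | 5/15 = 33.3% (11.8–61.6) | 4/15 = 26.7% (7.8–55.1) | 6.7 |
| 20 | 6/20 = 30.0% (11.9–54.3) | 5/20 = 25.0% (8.7–49.1) | 5.0 |
| 30 (all) | 9/30 = 30.0% (14.7–49.4) | 8/30 = 26.7% (12.3–45.9) | 3.3 |

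In each row one conversion decides whether the point estimate reaches 30%. Every interval contains 30% either way.

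**Step 4. Illustrative effect on the rate.** Assume an on-drug rate p = 25%, a share d of all subjects who stop unconverted, and a share q of those who convert later. The counted rate is p + d × q.

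- Low end, d = 10% and q = 5%: 0.25 + 0.10 × 0.05 = 25.5%.
- High end, d = 30% and q = 20%: 0.25 + 0.30 × 0.20 = 31.0%.

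The binomial chance of an observed rate of at least 30% rises from 31.4% to between 33.0% and 51.9% for n = 15 (at least 5 conversions), and from 32.6% to between 35.0% and 61.5% for n = 30 (at least 9). None of p, d or q comes from the documents.

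**The case against.** **No sentence says that off-drug visits count.** This stands. Table 3 sets dataset terminology, and SAP 9.2.1 does not refer to it. The visit list in SAP 2.1 includes Screening, so its wording is loose. Protocol 8.1.1 gives a treatment period of up to 48 weeks, and SAP Section 8 ends treatment days at the end of treatment. A programmer could therefore close the window at the last dose. Neither of those places is tied to the endpoint, however, and two workable readings of a primary variable are a reason to settle it.

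**Attendance after stopping is only encouraged.** This also stands. Protocol 9.3.1 allows a subject to be discontinued from assessments as well, so some who stop will contribute no later visits.

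**Off-drug conversion may be rare.** Protocol 6.2 expects no response to further NTM treatment in this population. Against that, Protocol 6.1 says the last positive culture rarely falls in the first six months of therapy, and Group 1 needs only six months of prior treatment. The question stays open.

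**Counting every scheduled visit is legitimate.** It is a treatment-policy approach and suits a single FAS. This stands, and it is why the primary rate need not be replaced. The choice should nevertheless be stated.

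**Listings already allow tracing.** The SAP lists stop dates (Section 6), conversion times (9.3.1.1) and flagged antimycobacterial changes (10.4). With 30 subjects this helps, but no output joins them.

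A reader might infer that early stoppers are favoured, since a subject who ends at Week 24 and declines the extension has 6 visits and 4 runs. The documents do not support that as a general statement: a Week 4 stopper has the same 10 runs as a 48-week completer, and the Week 24 group arises from the amendment that extended treatment.

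**Conclusion.** The point holds as a gap in the definition with a cheap remedy. The most direct reading of the two documents counts conversions that occur wholly after the last dose, and no planned output distinguishes them. In an uncontrolled trial this can raise the rate read as drug efficacy. Up to 9 of 10 runs can be off drug for one subject, and each such conversion is worth 6.7 points if a group has 15 subjects.

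Two stronger readings are tempting and do not hold.

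- A reader might infer that the rate is biased upwards by a material amount. The documents give no number of discontinuers and no off-drug conversion rate. They also do not establish that a conversion after dosing owes nothing to the drug; the durability endpoint itself looks at cultures 12 weeks after treatment.
- A reader might infer that the 30% comparison should move to an on-drug rate. SAP 9.3.1.1 attaches 30% to the primary endpoint. Moving it would replace the primary estimand, and background antibiotics confound on-drug conversions as well.

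No test against 30% is planned, so what could change is the descriptive reading of the point estimate.

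**What to change.** 1. **SAP 9.2.1.** Keep the all-scheduled-visits rate as the primary analysis, with the 30% mark attached to it. State that visits after drug discontinuation are included.
2. **SAP 9.3.1.2.** Add a sensitivity analysis of on-drug conversion, by group, with exact 95% intervals. All three qualifying visit dates must fall no later than the last dose date plus the 7-day visit window of Protocol Table 1. The allowance is needed because Protocol 11.5 puts the last dose on the day before the Week 48 visit, which should count for a completer.
3. **Pauses.** For subjects who stop after Week 24 and re-initiate under Version 4.0, visits during the off-drug interval do not contribute to a run. The simplest implementation restarts the run when dosing resumes.
4. **Kaplan-Meier.** In the matching time-to-conversion analysis, censor non-converters at their last on-drug visit.
5. **Smear conversion.** Apply the same rule in SAP 9.3.2.2.
6. **Reporting.** State how many primary converters had a run partly or wholly off drug.

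The cost is SAP wording and an extra table row. Treatment stop dates are already collected (SAP Section 6), and SAP Section 8 already identifies subjects with a break after Week 24. The on-drug rate may come out slightly lower than the primary rate.

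### The Kaplan-Meier analysis of time to conversion keeps 24-week-only subjects and early leavers at risk after their last possible event date, so the curve is equal to or below the correctly censored one

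*SAP*

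**What the plan says.** SAP 9.2.1 sets the event: "Sputum culture conversion during the treatment period defined as all available samples from three consecutive visits to be negative". It dates the event at the start of the run: "Defined as the time the first of three consecutive visits with 100% negative samples was obtained". Protocol 13.1 also dates conversion at the first of the three negatives. For subjects without an event, SAP 9.2.1 says: "Subjects with no conversion will be censored at the date of their last visit".

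SAP 9.3.1.1 then applies the product-limit method: "Time to culture conversion will be evaluated using Kaplan Meier estimates, with 95% confidence intervals". The same time-to-event analysis recurs in the culture sensitivity analysis (9.3.1.2), in smear conversion, which follows the culture analysis (9.3.2.1), and in the smear sensitivity analysis (9.3.2.2).

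Sputum visits are four-weekly: "at Weeks 4, 8, 12, 16, 20, 24, 28, 32, 36, 40, 44, and 48; Visits 1-14" (SAP 2.1). The same section provides for subjects who decline the extension. They "will end treatment after 24 weeks (visit 8) and will attend the follow-up visit 12-weeks later". SAP 3.3.2 (Table 3) places the follow-up visit in a separate epoch, after the treatment epoch. Nothing in the SAP limits censoring to the treatment period or to the last visit from which a three-visit run could still be seen.

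**The concern.** Kaplan-Meier divides the events at each time by the number of subjects who could have had an event recorded then. Here the event date looks forward: an event at one visit is known only if the next two visits are also negative. The censoring date takes no account of this. A subject whose treatment period ends early therefore sits in the denominator at visits where the definition allows no event for that subject.

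A time-to-event curve is the natural way to combine 24-week and 48-week subjects. If the shorter-followed subjects stay in the denominator, much of the adjustment for unequal follow-up is lost. Four curves inherit the rule, and protocol 6.3 says that the pilot's data are meant to inform the design of a later randomized trial.

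**Working it through.** The plan gives no Kaplan-Meier figure, event count or power statement to reproduce, so the check is on the rule itself.

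**Inputs from the documents**
- Sputum visits every 4 weeks, Weeks 4 to 48 (SAP 2.1).
- Event: three consecutive all-negative visits in the treatment period, dated at the first (SAP 9.2.1).
- Follow-up visit at 24 + 12 = Week 36 for 24-week-only subjects, and at 48 + 12 = Week 60 for 48-week subjects (SAP 2.1).
- 30 subjects in total (SAP 2.3).

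**Assumptions (not in the documents)**
- True conversion of 30%, with a constant chance at each possible event visit.
- Stopping unrelated to conversion.
- Share *f* of 24-week-only subjects from 10% to 50%.
- Dropout of 10% to 30%, spread evenly over last visits at Weeks 4 to 44.

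**Step 1: last possible event date.** A run of three visits spans 8 weeks, so the last possible date is the last treatment-period visit minus 8 weeks. For 48-week subjects this is 48 − 8 = Week 40. For 24-week-only subjects it is 24 − 8 = Week 16. The latter are censored at Week 36, so they count as at risk at Weeks 20, 24, 28, 32 and 36 with no event possible.

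**Step 2: direction.** Each Kaplan-Meier factor is 1 − d/n. The events d are the same under either censoring rule, and n under the SAP rule is never smaller. Each factor is therefore at least as large, and estimated conversion is equal or lower. For subjects who complete 48 weeks, the extra time at risk falls after Week 40, where d = 0 and every factor is 1. Censoring them at Week 40, 48 or 60 gives 30.0% each time.

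**Step 3: size from 24-week-only subjects.** Let q = 0.70^(1/10) = 0.9650, the chance of not converting at one of the ten possible visits.
- Weeks 4–16: everyone can convert; factor q⁴.
- Weeks 20–36: only the 48-week share can convert, but all are counted; factor f + (1 − f)q⁵.
- Week 40: the 24-week-only subjects have left; factor q.

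Estimated conversion = 1 − q⁵[f + (1 − f)q⁵]. With q⁵ = √0.70 = 0.8367 and q¹⁰ = 0.70, this is 0.30 − 0.1367f.

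| Share 24-week-only | SAP rule (Week 36) | Censor at Week 24 | Censor at Week 16 | Crude proportion |
|---|---|---|---|---|
| 10% | 28.6% | 29.5% | 30.0% | 28.3% |
| 20% | 27.3% | 29.0% | 30.0% | 26.7% |
| 33% | 25.4% | 28.3% | 30.0% | 24.4% |
| 50% | 23.2% | 27.4% | 30.0% | 21.6% |

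Read at Week 24, a true 19.3% appears as 18.7% (10% share) to 16.3% (50% share). Over true rates of 20% to 50% and the same shares, the Week 48 shortfall runs from 0.9 to 10.4 points.

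**Step 4: size from dropout alone.** A subject who leaves after visit m can have no event after visit m − 2 but is counted to m. With 10%, 20% or 30% dropout, a true 30% reads 29.5%, 29.0% or 28.4%. Censoring at m − 2 returns 30.0%. With 20% 24-week-only and 20% dropout together, the SAP rule gives 25.8%.

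**Step 5: example with 30 subjects (invented data).** Twenty subjects have 48 weeks and ten stop at Week 24. Seven conversions are dated at Weeks 8, 12, 16, 20, 24, 28 and 32; the one at Week 16 is in a 24-week-only subject.
- SAP rule: risk sets at Weeks 20/24/28/32 are 27/26/25/24. Survival is 23/30, so conversion is 23.3%, equal to the crude 7/30.
- Censoring at Week 16: risk sets are 18/17/16/15. Survival is 27/30 × 14/18 = 0.70, so conversion is 30.0%.

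**The case against.** **The estimand.** One can say that the lower curve is wrong only if the target is conversion had everyone stayed under observation in the treatment period, which the SAP does not state. If a 24-week non-converter is a failure, 23.3% in the example is a fair answer. It is true that the target is unstated. This does not rescue the rule: censoring at Week 36 removes these subjects from the denominator before Week 40, so they are not counted as failures to Week 48 either. In Step 3 the SAP-rule curve matches neither the crude proportion nor the correctly censored value.

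**Informative stopping.** Some 24-week-only subjects chose not to continue in an open-label trial. Correct censoring returns exactly 30.0% only because the model makes stopping non-informative, and with real data the corrected curve could err either way. That stands as a limit on the sizes. It does not affect Step 2, which compares two curves on the same events.

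**The meaning of treatment period.** SAP Table 3 assigns visits to the treatment epoch by visit number, and protocol 9.3.1 encourages subjects who stop drug to keep attending. If those visits count, such subjects can still have events, and censoring them at the end of dosing would discard usable follow-up. This stands, and the SAP must settle it.

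**Size.** At shares of 10% to 20% the shift is 1.4 to 2.7 points, less than one subject in 30, against an exact 95% interval of 14.7% to 49.4% for 9/30. Nothing in the documents supports the higher shares. If the last visit meant the last treatment-period visit, the loss would be smaller (the Week 24 column). The wording does not say that.

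**Conclusion.** The censoring rule does not match the event definition. In all four time-to-conversion curves it keeps some subjects at risk when no event can be dated for them. The curve is therefore equal to or below the correctly censored one. The effect comes only from subjects who end the treatment period or leave before Week 48, chiefly the 24-week-only group. Under a constant per-visit chance and non-informative stopping, a true 30% reads about 28.6% to 23.2% for 24-week-only shares of 10% to 50%, and about 29.5% to 28.4% for dropout of 10% to 30% alone. The actual shares are not given, so these are ranges and not predictions.

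A reader might infer three stronger things that the documents do not support:
- That the primary result is biased. The conversion rate with its exact binomial interval does not use the censoring date.
- That the SAP's 30% benchmark is compromised. It is set for that rate, not for the curve.
- That every non-converter adds to the error. Those who complete 48 weeks add none.

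The point merits correction because the rule is explicit and the repair is easy, but the primary analysis does not depend on it.

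**What to change.** Replace the censoring sentence in SAP 9.2.1. Keep the event date at the first negative visit, as in protocol 13.1. Censor non-converters at the last treatment-period sputum visit that is followed by two further consecutive treatment-period sputum visits, and exclude the 12-week follow-up visit from the risk period. Apply the same rule to smear conversion and to both sensitivity analyses.

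Add short statements on three matters:
- Whether visits after stopping drug count as treatment period.
- How subjects who restart after a break are handled (SAP 2.1 and 8.1.1), including whether a three-visit run may span the break.
- Whether 24-week non-converters are meant to count as failures. If so, keep them in the denominator through Week 48 instead of censoring them at Week 36.

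Dating events at the third negative visit is not an equivalent repair: it moves every event two visits (8 weeks) later and departs from protocol 13.1.

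The cost is one replaced sentence, the short clarifications and a small programming change. No new data are needed.
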